### Immune-Mediated Meningoencephalitis

Immune-mediated meningoencephalitis is an identified risk associated with the administration of atezolizumab. Immune-mediated meningoencephalitis should be suspected in any patient presenting with signs or symptoms suggestive of meningitis or encephalitis, including, but not limited to, headache, neck pain, confusion, seizure, motor or sensory dysfunction, and altered or depressed level of consciousness. Encephalopathy from metabolic or electrolyte imbalances needs to be distinguished from potential meningoencephalitis resulting from infection (bacterial, viral, or fungal) or progression of malignancy, or secondary to a paraneoplastic process.

All patients being considered for meningoencephalitis should be urgently evaluated with a CT scan and/or MRI scan of the brain to evaluate for metastasis, inflammation, or edema. If deemed safe by the treating physician, a lumbar puncture should be performed, and a neurologist should be consulted.

Patients with signs and symptoms of meningoencephalitis, in the absence of an identified alternate etiology, should be treated according to the guidelines in the table below.

Event	Management
Immune-related meningoencephalitis, all grades	
 
• Permanently discontinue atezolizumab.
 
• Refer patient to neurologist.
 
• Initiate treatment with corticosteroids equivalent to 1–2 mg/kg/day IV methylprednisolone and convert to 1–2 mg/kg/day oral prednisone or equivalent upon improvement.
 
• If event does not improve within 48 hours after initiating corticosteroids, consider adding an immunosuppressive agent.
 
• If event resolves to Grade 1 or better, taper corticosteroids over ≥1 month.
 

### Renal events

Immune-mediated nephritis has been associated with the administration of atezolizumab. Eligible patients must have adequate renal function. Renal function, including serum creatinine, should be monitored throughout study treatment. Patients with abnormal renal function should be evaluated and treated for other more common etiologies (including prerenal and postrenal causes, and concomitant medications such as non-steroidal anti-inflammatory drugs). Refer the patient to a renal specialist if clinically indicated. A renal biopsy may be required to enable a definitive diagnosis and appropriate treatment.

Patients with signs and symptoms of nephritis, in the absence of an identified alternate etiology, should be treated according to the guidelines in the table below.

Event	Management
Renal event, Grade 1	
 
Continue atezolizumab.
 
Monitor kidney function, including creatinine, closely until values resolve to within normal limits or to baseline values.
 

Renal event, Grade 2	
 
Withhold atezolizumab for up to 12 weeks after event onset.a
 
Refer patient to renal specialist.
 
Initiate treatment with corticosteroids equivalent to 1–2 mg/kg/day oral prednisone.
 
If event resolves to Grade 1 or better, resume atezolizumab.b
 
If event does not resolve to Grade 1 or better while withholding atezolizumab, permanently discontinue atezolizumab.
 

Renal event, Grade 3 or 4	
 
Permanently discontinue atezolizumab.
 
Refer patient to renal specialist and consider renal biopsy.
 
Initiate treatment with corticosteroids equivalent to 1–2 mg/kg/day oral prednisone.
 
If event does not improve within 48 hours after initiating corticosteroids, consider adding an immunosuppressive agent.
 
If event resolves to Grade 1 or better, taper corticosteroids over <math>\geq 1</math> month.
 

a Atezolizumab may be withheld for a longer period of time (i.e., >12 weeks after event onset) to allow for corticosteroids (if initiated) to be reduced to the equivalent of  $\leq 10$  mg/day oral prednisone. The acceptable length of the extended period of time must be determined by the investigator.

b If corticosteroids have been initiated, they must be tapered over  $\geq 1$  month to the equivalent of  $\leq 10$  mg/day oral prednisone before atezolizumab can be resumed.

### Immune-Mediated Myositis

Immune-mediated myositis has been associated with the administration of atezolizumab. Myositis or inflammatory myopathies are a group of disorders sharing the common feature of inflammatory muscle injury; dermatomyositis and polymyositis are among the most common disorders. Initial diagnosis is based on clinical (muscle weakness, muscle pain, skin rash in dermatomyositis), biochemical (serum creatine kinase increase), and imaging (electromyography/MRI) features, and is confirmed with a muscle biopsy.

Patients with signs and symptoms of myositis, in the absence of an identified alternate etiology, should be treated according to the guidelines in table below.

Event	Management
Immune-mediated myelitis, Grade 1	
 
Continue atezolizumab unless symptoms worsen or do not improve.
 
Investigate etiology and refer patient to a neurologist.
 

Immune-mediated myelitis, Grade 2	
 
Permanently discontinue atezolizumab.
 
Investigate etiology and refer patient to a neurologist.
 
Rule out infection.
 
Initiate treatment with corticosteroids equivalent to 1-2 mg/kg/day oral prednisone.
 

Immune-mediated myelitis, Grade 3 or 4	
 
Permanently discontinue atezolizumab.
 
Refer patient to a neurologist.
 
Initiate treatment as per institutional guidelines.
 

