### Neurologic disorders

Myasthenia gravis and Guillain-Barré syndrome have been observed with single agent atezolizumab. Patients may present with signs and symptoms of sensory and/or motor neuropathy. Diagnostic work-up is essential for an accurate characterization to differentiate between alternative etiologies. Management guidelines for neurologic disorders, and specific guidelines for myelitis, are provided in the table below.

Event	Management
Immune-mediated neuropathy, Grade 1	
 
• Continue atezolizumab.
 
• Investigate etiology.
 
• Any cranial nerve disorder (including facial paresis) should be managed as per Grade 2 management guidelines below.
 

Immune-mediated neuropathy, including facial paresis, Grade 2	
 
• Withhold atezolizumab for up to 12 weeks after event onset. a
 
• Investigate etiology and refer patient to neurologist.
 
• Initiate treatment as per institutional guidelines.
 
• For general immune-mediated neuropathy:               
 
○ If event resolves to Grade 1 or better, resume atezolizumab. b
 
○ If event does not resolve to Grade 1 or better while withholding atezolizumab, permanently discontinue atezolizumab. c
 
 
 
• For facial paresis:               
 
○ If event resolves fully, resume atezolizumab. b
 
○ If event does not resolve fully while withholding atezolizumab, permanently discontinue atezolizumab. c
 
 
 

Immune-mediated neuropathy, including facial paresis, Grade 3 or 4	
 
• Permanently discontinue atezolizumab. c
 
• Refer patient to neurologist.
 
• Initiate treatment as per institutional guidelines.
 

Event	Management
Myasthenia gravis and Guillain-Barré syndrome (any grade)	
 
• Permanently discontinue atezolizumab.c
 
• Refer patient to neurologist.
 
• Initiate treatment as per institutional guidelines.
 
• Consider initiation of corticosteroids equivalent to 1–2 mg/kg/day oral or IV prednisone.
 

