a Atezolizumab may be withheld for a longer period of time (*i.e.*, >12 weeks after event onset) to allow for corticosteroids (if initiated) to be reduced to the equivalent of ≤10 mg/day oral prednisone. The acceptable length of the extended period of time must be based on an assessment of benefit–risk by the investigator and in alignment with the protocol requirements for the duration of treatment and documented by the investigator.

b If corticosteroids have been initiated, they must be tapered over ≥1 month to the equivalent of ≤10 mg/day oral prednisone before atezolizumab can be resumed.

c Resumption of atezolizumab may be considered in patients who are deriving benefit and have fully recovered from the immune-mediated event. The decision to re–challenge patients with atezolizumab should be based on investigator's assessment of benefit–risk and documented by the investigator (or an appropriate delegate).

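### Section 8.2.2 sends myositis patients to a table whose three rows are all labelled myelitis, and the table that promises myelitis guidance has no myelitis row

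*Combined protocol and SAP*

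**What the plan says.** Two places in Section 8.2.2 (Dose Modifications for Atezolizumab) matter.

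- **Immune-Mediated Myositis.** The text describes inflammatory muscle disease, with weakness, raised creatine kinase and muscle biopsy. It then gives the instruction "Patients with signs and symptoms of myositis, in the absence of an identified alternate etiology, should be treated according to the guidelines in table below". The three row labels that follow are "Immune-mediated myelitis, Grade 1", "Immune-mediated myelitis, Grade 2" and "Immune-mediated myelitis, Grade 3 or 4".
- **Neurologic disorders.** The text says "Management guidelines for neurologic disorders, and specific guidelines for myelitis, are provided in the table below". The table has four rows: neuropathy Grade 1; neuropathy with facial paresis Grade 2; the same at Grade 3 or 4; and myasthenia gravis with Guillain-Barré syndrome at any grade.

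Elsewhere the protocol keeps the two events apart. The risk list under Management of Specific AEs names both. The CAEPR in Section 9.4 puts myositis under musculoskeletal disorders and immune-mediated myelitis under nervous system disorders.

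**The concern.** Myositis is inflammation of muscle and myelitis is inflammation of the spinal cord. A site with a myositis patient is sent to rows that name the other event. A site with a myelitis patient that follows the Neurologic disorders text finds no row where it was told to look.

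The rows decide whether atezolizumab is continued or stopped for good, so the label matters to patients. Section 8.2.2 also says that myocarditis may be a manifestation of myositis, so an unclear myositis rule can bear on the handling of a cardiac event.

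**Working it through.** There is no figure to reproduce. The check is a comparison of the text.

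**1. Count the labels.** In the table under the myositis heading, 3 of 3 rows say myelitis and 0 say myositis. In the Neurologic disorders table, 0 of 4 rows say myelitis; the text after it holds only footnotes. No row anywhere in Section 8.2.2 is labelled myositis.

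**2. Rule out a reading error from the PDF.** The word myelitis is printed in three separate labels. Complete meningoencephalitis and renal sections stand between the two tables, so the rows did not slip from one table to the next in extraction.

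**3. Ask whether the rows are misplaced or only mislabelled.**

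- *For misplaced:* the Neurologic disorders text promises myelitis guidance that is absent there. The Grade 3 or 4 row gives the same three instructions (stop permanently, refer to a neurologist, treat by institutional practice) as the row "Immune-mediated neuropathy, including facial paresis, Grade 3 or 4".
- *Not decisive:* the instruction "Investigate etiology and refer patient to a neurologist" in the Grade 1 and 2 rows also fits myositis, because the myositis text itself names electromyography in the work-up. Ruling out infection at Grade 2 fits too, because Section 9.1.2 has infective myositis among the events to solicit.
- *Result:* open. The documents do not say which error was made.

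**4. Compare what a site would do for a myositis patient under each reading.** The last column uses General AE Management and Dose Modification Guidelines in Section 8.2.2.

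| Grade | Rows applied to myositis (read literally, or as mislabelled) | Rows judged misplaced: general rule |
|---|---|---|
| 1 | Continue unless symptoms worsen or fail to improve | Continue |
| 2 | Stop permanently; steroids at 1–2 mg/kg/day prednisone equivalent | Generally continue; recurrent events may lead to a hold or steroids |
| 3 | Stop permanently; treat by institutional practice | Withhold; give steroids |
| 4 | Stop permanently; treat by institutional practice | Stop permanently, taking Grade 4 as life-threatening |

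The atezolizumab decision differs at Grades 2 and 3 only, and only for a site that judges the rows misplaced.

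**5. Check re-challenge.** The neuropathy Grade 3 or 4 row carries a footnote: "Resumption of atezolizumab may be considered in patients who are deriving benefit and have fully recovered from the immune-mediated event". The three rows under the myositis heading do not carry it. If they belong in the neurologic table, whether that footnote applies must be stated.

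**The case against.** The strongest case is that neither event lacks a rule. The myositis text points directly at its table, and that table gives an action at every grade. Myelitis has labelled rows at every grade too, a little further on in the same section. A site that sees a mere labelling slip applies the rows as printed, which gives the same action as a literal reading and the more cautious one for atezolizumab. All of this stands, and it narrows the consequence.

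A reader might infer more than the documents support:

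- *That myositis has no specific rule and only the general guidance applies.* The text expressly directs myositis patients to the table, so this follows only if a site sets that instruction aside.
- *That the rows are proven to be misplaced.* The evidence leans that way but also fits a labelling error.
- *That departing from the general guidance is itself an error.* Specific tables in Section 8.2.2 routinely override it. The comparison shows only what depends on the label.

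The timing objection also has force. Arm 1 treatment lasts 12 months. Appendix IV, section 1.5, planned last treatment in Germany for February 2023, and the expedited reporting text in Section 9.3.1 carries an effective date of August 30, 2024. Treatment dates for other sites are not given. Against that, the nursing guidelines in Section 10.5 say effects may appear months after stopping, so the referral and steroid instructions can outlast dosing.

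The Investigator's Brochure may hold the intended rule, but it cannot be checked here. The topics for which Management of Specific AEs cites it include neither myositis nor myelitis by name.

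**Conclusion.** The table is wrong as written. This is an internal inconsistency in an Arm 1 safety table, not a design choice, and it should be corrected. It consists of three wrong labels or three misplaced rows, plus one promise of myelitis guidance that the neurologic table does not keep.

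The effect on treatment is limited to Grade 2 and 3 myositis at sites that judge the rows misplaced, and to myelitis patients whose site looks only where the Neurologic disorders text points. Few patients are affected. The CAEPR puts both events in its rare-but-serious category, below 3%, with frequencies based on 3097 patients. That is a category ceiling, not a rate for this combination, and the documents give no such rate. There is no effect on alpha, power or endpoints.

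The conclusion rests on the printed labels and on the protocol's own separation of the two events. It does not depend on which of the two errors was made.

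**What to change.** The sponsor first checks the three rows against the source atezolizumab toxicity guidance.

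- **If they are myelitis rows:** move them to the Neurologic disorders table and state whether the re-challenge footnote (c) applies. In the same update, print the grade-by-grade myositis rows under the myositis heading, so that myositis is never left without a rule.
- **If only the labels are wrong:** relabel the three rows as myositis and add the promised myelitis rows to the Neurologic disorders table.

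In both cases leave the general guidance unchanged. The cost is one check and a text correction in the next protocol update, with no statistical cost. If Arm 1 treatment has ended, the gain for dosing is limited, and what remains is clear guidance for late events and a correct record of the rule.

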### Hemophagocytic Lymphohistiocytosis and Macrophage Activation Syndrome

Immune-mediated reactions may involve any organ system and may lead to hemophagocytic lymphohistiocytosis (HLH) and macrophage activation syndrome (MAS).

Patients with suspected HLH should be diagnosed according to published criteria by McClain and Eckstein (2017). A patient should be classified as having HLH if five of the following eight criteria are met:

- Fever  $\geq 38.5^{\circ}\text{C}$
- Splenomegaly
- Peripheral blood cytopenia consisting of at least two of the following:
  - Hemoglobin  $< 90 \text{ g/L}$  ( $9 \text{ g/dL}$ ) ( $<100 \text{ g/L}$  [ $10 \text{ g/dL}$ ] for infants  $< 4$  weeks old)
  - Platelet count  $< 100 \times 10^9/\text{L}$  ( $100,000/\text{mcL}$ )
  - ANC  $< 1.0 \times 10^9/\text{L}$  ( $1000/\text{mcL}$ )
- Fasting triglycerides  $>2.992 \text{ mmol/L}$  ( $265 \text{ mg/dL}$ ) and/or fibrinogen  $<1.5 \text{ g/L}$  ( $150 \text{ mg/dL}$ )
- Hemophagocytosis in bone marrow, spleen, lymph node, or liver
- Low or absent natural killer cell activity
- Ferritin  $>500 \text{ mg/L}$  ( $500 \text{ ng/mL}$ )
- Soluble interleukin 2 (IL-2) receptor (soluble CD25) elevated  $\geq 2$  standard deviations above age-adjusted laboratory-specific norms

Patients with suspected MAS should be diagnosed according to published criteria for systemic juvenile idiopathic arthritis by Ravelli *et al.* (2016). A febrile patient should be classified as having MAS if the following criteria are met:

- Ferritin  $>684 \text{ mg/L}$  ( $684 \text{ ng/mL}$ )
- At least two of the following:
  - Platelet count  $\leq 181 \times 10^9/\text{L}$  ( $181,000/\text{mcL}$ )
  - AST  $\geq 48 \text{ U/L}$
  - Triglycerides  $>1.761 \text{ mmol/L}$  ( $156 \text{ mg/dL}$ )
  - Fibrinogen  $\leq 3.6 \text{ g/L}$  ( $360 \text{ mg/dL}$ )

Patients with suspected HLH or MAS should be treated according to the guidelines in below.

Event	Management
Suspected HLH or MAS	
 
• Permanently discontinue atezolizumab and contact Medical Monitor.
 
• Consider patient referral to hematologist.
 
• Initiate supportive care, including intensive care monitoring if indicated per institutional guidelines.
 
• Consider initiation of IV corticosteroids and/or an immunosuppressive agent.
 
• If event does not improve within 48 hours after initiating corticosteroids, consider adding an immunosuppressive agent.
 
• If event resolves to Grade 1 or better, taper corticosteroids over <math>\geq 1</math> month.
 

HLH=hemophagocytic lymphohistiocytosis; MAS=macrophage activation syndrome.

## 9.0 ADVERSE EVENTS

The prompt reporting of adverse events is the responsibility of each investigator engaged in clinical research, as required by Federal Regulations. Beginning April 1, 2018, adverse events must be described and graded using the terminology and grading categories defined in the NCI's Common Terminology Criteria for Adverse Events (CTCAE), Version 5.0. The CTCAE is available at [ctep.cancer.gov/protocolDevelopment/electronic\\_applications/ctc.htm](http://ctep.cancer.gov/protocolDevelopment/electronic_applications/ctc.htm). Attribution to protocol treatment for each adverse event must be determined by the investigator and reported on the required forms. Please refer the NCI Guidelines: Adverse Event Reporting Requirements for further details on AE reporting procedures.

To complement CTCAE reporting, patients aged  $\geq 18$  years will self-report their side effects using the PRO-CTCAE. The specific PRO-CTCAE items for this protocol can be found in [Appendix I](#). They can also be found at: <http://healthcaredelivery.cancer.gov/pro-ctcae/instrument.html>.

**NOTE:** PRO-CTCAE data should not be used for determining attribution, dose modifications, or reporting of serious adverse events.

### 9.1 Routine Adverse Event Reporting

Adverse event data collection and reporting, which are required as part of every clinical trial are done to ensure the safety of patients enrolled in the studies as well as those who will enroll in future studies using similar agents. Adverse events are reported in a routine manner at scheduled times according to the Study Calendar in [Section 5.0](#). For this trial, the Form "Adverse Events" is used for routine AE reporting in Rave.

#### 9.1.1 Rave-CTEP-AERS integration

The Rave Cancer Therapy Evaluation Program Adverse Event Reporting System (CTEP-AERS) integration enables evaluation of post-baseline Adverse Events (AE) entered in Rave to determine whether they require expedited reporting and facilitates entry in CTEP-AERS for those AEs requiring expedited reporting.

All AEs that occur after start of treatment are collected in Medidata Rave using the Adverse Event form, which is available for entry at each treatment course or reporting period, and used to collect AEs that start during the period or persist from the previous reporting period. AEs that occur 30 days after the last administration of the investigational agent/intervention are collected using the Late Adverse Event form.

The CRA will enter AEs that occur prior to the start of treatment on a baseline form that is not included in the Rave-CTEP-AERS integration. AEs that occur prior to enrollment must begin and end on the baseline Adverse Events form and should not be included on the standard Adverse Events form that is available at treatment unless there has been an increase in grade.

Prior to sending AEs through the rules evaluation process, site staff should verify the following on the Adverse Event form in Rave:

- The reporting period (course/cycle) is correct; and
- AEs are recorded and complete (no missing fields) and the form is query free.

The CRA reports AEs in Rave at the time the Investigator learns of the event. If the CRA modifies an AE, it must be re-submitted for rules evaluation.

Upon completion of AE entry in Medidata Rave, the CRA submits the AE for rules evaluation by completing the Expedited Reporting Evaluation form. Both NCI and protocol-specific reporting rules evaluate the AEs submitted for expedited reporting. A report is initiated in CTEP-AERS using information entered in Medidata Rave for AEs that meet reporting requirements. The CRA completes the report by accessing CTEP-AERS via a direct link on the Medidata Rave Expedited Reporting Evaluation form. Contact the CTSU Help Desk at [name] or by email at [[contact]](mailto:[contact]) if you have any issues submitting an expedited report in CTEP-AERS.

In the rare occurrence that Internet connectivity is lost, a 24-hour notification is to be made to CTEP by telephone at [contact]. Once Internet connectivity is restored, the 24-hour notification that was phoned in must be entered immediately into CTEP-AERS using the direct link from Medidata Rave.

Additional information about the CTEP-AERS integration is available on the CTSU website:

- Study specific documents: *Protocols > Documents > Protocol Related Documents > Adverse Event Reporting*; and
- Additional resources: *Resources > CTSU Operations Information > User Guides & Help Topics*.
- NCI requirements for SAE reporting are available on the CTEP website:
- NCI Guidelines for Investigators: Adverse Event Reporting Requirements is available at [https://ctep.cancer.gov/protocolDevelopment/electronic\\_applications/docs/aeguidelines.pdf](https://ctep.cancer.gov/protocolDevelopment/electronic_applications/docs/aeguidelines.pdf)

PRO-CTCAE paper booklets ordered from the CTSU website are to be administered by a nurse/CRA and completed by the patient at scheduled times according to the Study Calendar in [Section 5.0](#) and entered into Rave.

**9.1.2 Solicited Adverse Events**

The following adverse events are considered "expected" and their presence/absence should be solicited, and severity graded, at baseline and for each cycle of treatment by CTCAE, PRO-CTCAE, or both.

**NOTE:** PRO-CTCAE data should not be used for determining attribution, dose modifications, or reporting of serious adverse events.

CTCAE v5.0 Term	PRO-CTCAE v1.0 Term	CTCAE v5.0 System Organ Class (SOC)
The following adverse events should be solicited at baseline and for each treatment cycle:		
Hypothyroidism		Endocrine disorders
Abdominal Pain	Pain in the abdomen (belly area)	Gastrointestinal disorders
Constipation	Constipation	Gastrointestinal disorders
Nausea	Nausea	Gastrointestinal disorders
Fatigue	Fatigue, tiredness, or lack of energy	General disorders and administration site conditions
Anorexia	Decreased appetite	Metabolism and nutrition disorders
Cough	Cough	Respiratory, thoracic, and mediastinal disorders
Dyspnea	Shortness of breath	Respiratory, thoracic, and mediastinal disorders
Fever		General disorders
Blood bilirubin increased		Investigations
Neutrophil count decreased		Investigations
Platelet count decreased		Investigations
	Loose or watery stools (diarrhea)	Gastrointestinal disorders
	Vomiting	Gastrointestinal disorders
	Numbness or tingling in your hands or feet	Nervous system disorders

CTCAE v5.0 Term	PRO-CTCAE v1.0 Term	CTCAE v5.0 System Organ Class (SOC)
	Heartburn	Gastrointestinal disorders
Palmar-plantar erythrodysesthesia syndrome	Hand-foot syndrome (a rash of the hands or feet that can cause cracking, peeling, redness, or pain)	Skin and subcutaneous tissue disorders
	Rash	Skin and subcutaneous tissue disorders
	Itchy skin	Skin and subcutaneous tissue disorders
	Mouth or throat sores	Gastrointestinal disorders
The following adverse events should be solicited as clinically indicated*:		
Alanine aminotransferase increased 		Investigations
Aspartate aminotransferase increased 		Investigations
Hepatitis		Infections and infestations
Encephalitis infection		Infections and infestations
Kidney infection		Infections and infestations
Infective myositis		Infections and infestations
Infections and infestations – Other, specify 		Infections and infestations
Pneumonitis		Respiratory, thoracic, and mediastinal disorders
Colitis		Gastrointestinal disorders
Pancreatitis		Gastrointestinal disorders
Hyperglycemia		Metabolism and nutrition disorders
Hyperthyroidism		Endocrine disorders

CTCAE v5.0 Term	PRO-CTCAE v1.0 Term	CTCAE v5.0 System Organ Class (SOC)
Adrenal insufficiency		Endocrine disorders
Hypophysitis		Endocrine disorders
Blood and lymphatic system disorders – Other, specify		Blood and lymphatic system disorders
Autoimmune disorder 		Immune system disorders
Cytokine release syndrome 		Immune system disorders
Immune system disorders – Other, specify 		Immune system disorders
Flu like symptoms 		General disorders and administration site conditions
Uveitis		Eye disorders
Retinopathy		Eye disorders
Generalized muscle weakness 		Musculoskeletal and connective tissue disorders
Rhabdomyolysis		Musculoskeletal and connective tissue disorders
Musculoskeletal and connective tissue disorder – Other, specify 		Musculoskeletal and connective tissue disorders
Atrial fibrillation		Cardiac disorders
Myocarditis		Cardiac disorders
Pericarditis		Cardiac disorders
Vasculitis		Vascular disorders

\* If the AE is not clinically indicated, then its presence/absence would not need to be solicited for that time point.

AEs of special interest have been incorporated above, please note the clarifications below:

1. Cases of potential drug-induced liver injury that include an elevated ALT or AST in combination with either an elevated bilirubin or clinical jaundice, as defined by Hy's Law and based on the following observations:

- a. Treatment-emergent ALT or AST > 3 x baseline value in combination with total bilirubin > 2 x ULN (of which > 35% is direct bilirubin)
  - b. Treatment-emergent ALT or AST > 3 x baseline value in combination with clinical jaundice
2. Suspected transmission of an infectious agent by the study treatment, as defined below:
  - a. Any organism, virus, or infectious particle (e.g. prion protein transmitting transmissible spongiform encephalopathy), pathogenic or non-pathogenic, is considered an infectious agent. A transmission of an infectious agent may be suspected from clinical symptoms or laboratory findings that indicate an infection in a patient exposed to a medicinal product. This term applies only when a contamination of study treatment is suspected.
3. Neurological Disorders: Guillain-Barré syndrome, myasthenic syndrome or myasthenia gravis, and meningoencephalitis
4. Events suggestive of hypersensitivity, infusion-related reactions, cytokine release syndrome, influenza-like illness, macrophage activation syndrome, hemophagocytic lymphohistiocytosis

